9.5.3. Suicide-Related Thoughts and Behaviors

Suicidal ideation, suicidal behavior, and non-suicidal self-injurious behavior based on the C-SSRS will be summarized by treatment group. For each of the following events, the number and percentage of patients with the event will be enumerated by treatment: completed suicide, non-fatal suicide attempt, interrupted attempt, aborted attempt, preparatory acts or behavior, active suicidal ideation with specific plan and intent, active suicidal ideation with some intent to act without specific plan, active suicidal ideation with any methods (not plan) without intent to act, non-specific active suicidal thoughts, wish to be dead, and non-suicidal self-injurious behavior.

In addition, the number and percentage of patients who experienced at least one of the composite measures during Study Period III, Study Period IV, and Study Period V separately will be presented and compared. These include suicidal acts (completed suicide and nonfatal suicidal attempts), suicidal behavior (suicidal acts, interrupted attempts, aborted attempts, and preparatory acts or behavior), treatment-emergent suicidal ideation or treatment-emergent suicidal behavior.

The Fisher's exact test will be used for treatment comparisons.

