^a The eligibility period of the prospective baseline assessment will last from 30 to 40 days. Investigators and patients may have up to an additional 5 days to schedule their Visit 3 appointment (beyond the 40 days); however, eligibility will be based on the 30- to 40-day period.

^b Visit is to include a review of any spontaneously reported adverse events and collection of blood samples for immunogenicity, PK, and CGRP plasma.

^c A neurological exam will be conducted at screening, Month 3 (final visit of double-blind treatment), Months 6, 9, and 12 (open-label treatment), and Month 16/early termination in order to assess for any signs of pre-existing or treatment-emergent neurological abnormalities such as stroke or other cerebrovascular events.

^d Electrocardiograms (ECGs) will be performed at Visit 1, Visit 3, Visit 7, Visit 10, Visit 16, and Visit 18 or early termination. Note: The Visit 3 ECG should be collected prior to blood draws and dosing. Patients must be supine for approximately 5 to 10 minutes before ECG collection and remain supine but awake during ECG collection.

^e Vital signs taken at every office visit will include body temperature, blood pressure and pulse. Blood pressure and pulse will be measured in triplicate in the sitting position and should be measured prior to blood draws. Blood pressure will be assessed by utilizing a calibrated machine.

^f Chemistry labs collected at Visit 3, Visit 7, Visit 10, Visit 13, Visit 16, and Visit 18 or early termination must be fasting. Fasting is defined as no food or drink, except water, for at least 8 hours prior to testing.

g In the event of a positive urine leukocyte esterase result, a repeat urine sample will be collected and shipped to the central laboratory.

^h A positive urine test must be followed by a serum pregnancy test for confirmation.

Immunogenicity and storage sample, and PK blood sampling to be performed at the indicated visits and prior to dose administration if the visit is a dosing visit. Samples will be taken in the event of early termination. Immunogenicity samples also may be collected in the event of a systemic allergic/hypersensitivity reaction (see Section 8.4.3). The exact date and time of the samples should be recorded.

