5.5.1.5. Baseline and Postbaseline Definition

Table CGAI.5.4 describes the rules for determining the patient population and baseline and postbaseline observations for each study phase and type of analysis. When "last of Visit x-x" is used in the table, the last nonmissing observation obtained in the visit interval will be used.

Table CGAI.5.4. Patient Population with Baseline and Postbaseline Definitions by Study Period and Type of Analysis

Study Period / Analysis	Patient Population	Baseline Observation	Postbaseline Observation(s)
Study Period III			
Efficacy analyses (Repeated Measures) or average of observed monthly values	ITT Population with a baseline and at least 1 postbaseline observation	Visit 3	All scheduled visits 3 < Visits ≤7
Efficacy analyses at LOCF endpoint		Visit 3	Last of Visit 3.01-7
Quality of Life analyses (Repeated Measures)		Visit 3	All scheduled visits 3 < Visits ≤7
Quality of Life analyses at LOCF endpoint or for average of observed monthly values		Visit 3	Last of Visit 3.01-7
TEAEs	Safety Population	All Visits 1–3	All Visits 3.01–7
Serious Adverse Events, Discontinuations due to Adverse Events	Safety Population	NA	All Visits 3.01–7
C-SSRS categorical analyses	Patients with a baseline and at least 1 postbaseline C-SSRS assessment	Recent History: Visits 1–3 excluding lifetime ^a All Prior History: Visits 1–3 including lifetime ^a	All Visits 3.01–7
Treatment-emergent abnormal laboratory values	Safety Population with normal laboratory values at all nonmissing baseline visits (with respect to direction being analyzed) and who have at least 1 postbaseline observation	Low: Minimum from Visits 1–3 High: Maximum from Visits 1–3 Abnormal: All Visits 1–3	Low: Minimum from Visits 3.01–7 High: Maximum from Visits 3.01–7 Abnormal: All Visits 1–3
Treatment-emergent immunogenicity	Safety Population	Visit 3	All Visits 3.01–7
Treatment-emergent changes in temperature and weight	Safety Population with a baseline and at least 1 postbaseline observation	Low: Minimum from Visits 1–3 High: Maximum from Visits 1–3	Low: Minimum from Visits 3.01–7 High: Maximum from Visits 3.01–7
Treatment-emergent changes in blood pressures, pulse, and ECGs	Safety Population with a baseline and at least 1 postbaseline observation	Low: Last non-missing from Visits 1–3 High: Last non-missing from Visits 1–3	Low: Minimum from Visits 3.01–7 High: Maximum from Visits 3.01–7

Patient Population with Baseline and Postbaseline Definitions by Study Period and Type of Analysis

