5.5.12.1.2. Suicide-Related Thoughts and Behaviors

Suicidal ideation, suicidal behavior, and self-injurious behavior without suicidal intent occurring during treatment, based on the C-SSRS, will be summarized by treatment. In particular, for each of the following events, the number and percent of patients with the event will be enumerated by treatment: completed suicide, nonfatal suicide attempt, interrupted attempt, aborted attempt, preparatory acts or behavior, active suicidal ideation with specific plan and intent, active suicidal ideation with some intent to act without specific plan, active suicidal ideation with any methods (no plan) without intent to act, nonspecific active suicidal thoughts, wish to be dead, and self-injurious behavior without suicidal intent.

In addition, the number and percent of patients who experienced at least 1 of various composite measures will be presented and compared. These include suicidal behavior (completed suicide, non-fatal suicidal attempts, interrupted attempts, aborted attempts, and preparatory acts or behavior), suicidal ideation (active suicidal ideation with specific plan and intent, active suicidal ideation with some intent to act without specific plan, active suicidal ideation with any methods [no plan] without intent to act, non-specific active suicidal thoughts, and wish to be dead), and suicidal ideation or behavior.

The number and percent of patients who experienced at least 1 of various comparative measures during treatment will be summarized and compared for SP III, and summarized for SP IV and SP V. These include treatment-emergent suicidal ideation compared to recent history, treatment-emergent serious suicidal ideation compared to recent history, emergence of serious suicidal ideation compared to recent history, improvement in suicidal ideation at endpoint compared to baseline, and emergence of suicidal behavior compared to all prior history.

Specifically, the following outcomes are C-SSRS categories and have binary responses (yes/no). The categories have been re-ordered from the actual scale to facilitate the definitions of the composite and comparative endpoints, and to enable clarity in the presentation of the results.

Category 1 – Wish to be Dead

Category 2 – Non-specific Active Suicidal Thoughts

Category 3 – Active Suicidal Ideation with Any Methods (Not Plan) without Intent to Act

Category 4 – Active Suicidal Ideation with Some Intent to Act, without Specific Plan

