Patients who discontinued from the study with no postbaseline C-SSRS value will be considered unevaluable for analyses of suicide-related events. Only evaluable patients will be considered in the analyses. The CMH test will be used for treatment comparisons. For each event, p-values will only be displayed if at least 4 events occurred in at least 1 treatment group.

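### The suicide table counts events only from the C-SSRS and only in patients with a postbaseline C-SSRS, so a suicide, or an attempt by a patient who never returns, before a period's first interview can drop out of it

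*SAP*

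**What the plan says.** SAP 5.5.12.1.2 names the data source: "Suicidal ideation, suicidal behavior, and self-injurious behavior without suicidal intent occurring during treatment, based on the C-SSRS, will be summarized by treatment". The events to be counted include "completed suicide, nonfatal suicide attempt, interrupted attempt, aborted attempt, preparatory acts or behavior". Completed suicide is Category 10, and the suicidal behavior composite is a yes to any of Categories 6 to 10 on the instrument.

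The section ends with an exclusion: "Patients who discontinued from the study with no postbaseline C-SSRS value will be considered unevaluable for analyses of suicide-related events", followed by "Only evaluable patients will be considered in the analyses". The SP III row of Table CGAI.5.4 (SAP 5.5.1.5) defines the population for the categorical C-SSRS analyses as "Patients with a baseline and at least 1 postbaseline C-SSRS assessment". The SP IV and SP V rows add the same condition to their own populations. None of these places makes an exception for a death, or for an event known from AE or SAE reporting.

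Protocol 9.5.3 also bases the summary on the C-SSRS and lists the same count ("the number and percentage of patients with the event will be enumerated by treatment: completed suicide"), but it has no evaluability exclusion. The SAP revision history gives no reason for adding one.

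The footnotes to the Schedule of Activities (Protocol Appendix 2) place the C-SSRS at scheduled and unscheduled office visits. For Visit 4 they say: "Visit is to include a review of any spontaneously reported adverse events and collection of blood samples for immunogenicity, PK, and CGRP plasma". The C-SSRS is not mentioned there.

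**The concern.** Requiring a postbaseline interview is reasonable for an ideation score, because without an interview there is no score. Completed suicide is different: the event itself prevents the interview. A patient who makes an attempt and is never seen again is in a similar position. For these outcomes the rule does not handle ordinary missing data. It can remove a patient because of the event being counted.

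Suicidality is a named safety endpoint in both documents, and a single event matters in such a table. It could show no completed suicide in an arm whose SAE listing contains one, and a reader of the suicide table alone would be misled.

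**Working it through.** The plan gives no figure to reproduce, so the check traces the rule for one patient and then measures the window.

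**Tracing the rule.** Take a patient who is dosed at Visit 3 and dies by suicide before the next C-SSRS.

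1. Source. The count comes from the C-SSRS (SAP 5.5.12.1.2). The section names no SAE or death record as a second source.
2. Opportunity. The C-SSRS is completed at office visits (Protocol Appendix 2 footnote). The patient attends none after Visit 3, and no completion after death is described.
3. Evaluability. With no postbaseline value the patient is unevaluable under 5.5.12.1.2 and outside the SP III population of Table CGAI.5.4. The sentence in 5.5.12.1.2 concerns patients who discontinued; the table has no such limit.
4. Other tables. The SAE and AE-discontinuation row for SP III in Table CGAI.5.4 uses the Safety Population (all randomized and dosed patients) with no C-SSRS condition. Death is an SAE outcome (Protocol 8.2.1), so the event is reported there.
5. Deviation check. The check for missing C-SSRS in the double-blind phase (SAP section 7) applies only to patients with a Visit 5 date and exempts those lost to follow-up. It would not flag this patient, or an attempter lost before Visit 5.

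Steps 1 to 3 give the omission. Step 4 shows that it is confined to the suicide table.

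**Length of the window** (target intervals and allowances from the Schedule of Activities):

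| Period | From – to | Target days | With allowances |
|---|---|---|---|
| SP III | Visit 3 – Visit 5 | 14 + 16 = 30 | 30 ± (1 + 3) = 26 to 34 |
| SP IV | Visit 7 – Visit 8 | 30 | 28 to 32 |
| SP V | Visit 16 – Visit 17 | 60 | 55 to 65 |

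The SP III row assumes no C-SSRS at Visit 4. The C-SSRS line of the double-blind schedule cannot be read in the text available, so this is inferred from the Visit 4 footnote; the Visit 5 condition in the deviation check points the same way. An unscheduled visit with a C-SSRS would shorten any of these windows.

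**Illustration of one event.** An active arm has about 285 patients (SAP 5.2). One suicide inside the window:

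- under the SAP rule: 0/(285 − 1) = 0/284 = 0%
- with the event counted in the dosed population: 1/285 = 0.35%

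The documents give no expected rate of suicidal events, so the expected number affected cannot be calculated.

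**The case against.** The strongest reply is that the evaluability sentence is not the real cause. Category 10 is a yes/no item that a deceased patient never answers. Either site staff enter it after the death, in which case that entry is itself a postbaseline C-SSRS value and the patient is counted; or nobody enters it, in which case no suicide is counted at any time, including in patients already interviewed. This stands in part. A late entry would restore the patient, but the documents do not provide for one and the office-visit footnote points the other way. The second branch makes a count drawn only from the C-SSRS worse, not sound. It also means that the windows above show where the evaluability rule acts on its own, not the only time at which an event could be missed.

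Other points narrow the concern and are accepted:

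- The death is not lost to safety reporting. A reader might infer that suicides vanish from the trial's safety results; the SAE and discontinuation analyses and the registry summary (SAP 5.9) do not support that.
- A reader might infer that every early attempter is dropped. Patients who stop early have termination procedures, and the early-termination column includes the C-SSRS. Only an attempter who never returns is affected.
- The window is calendar time and should not be read as a share of events lost. A patient with a later C-SSRS in the same period stays evaluable.
- Such events should be rare: exclusion criterion 28 removes patients at significant suicide risk. P-values appear only with at least 4 events in a group, so one event alone would not produce a test.

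The schedule also lists self-harm supplement and follow-up forms. Their content is not shown, and 5.5.12.1.2 does not use them as a source.

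**Conclusion.** The concern holds for the suicide table. As written, SAP 5.5.12.1.2 and Table CGAI.5.4 can leave out a completed suicide, or an attempt by a patient who never returns, when it falls before the first C-SSRS of a period, and the patient leaves the denominator too. This rests on two assumptions: that no C-SSRS record is entered after the event, and, for the 30-day figure in SP III, that none is done at Visit 4.

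The numerical effect is probably small and cannot be estimated from the documents. The defect is that the exclusion depends on the outcome, in a table where one event is informative, and that the result could disagree with the SAE table. It does not bear on the efficacy conclusions. The documents do not support a stronger claim, either that such events disappear from all safety reporting or that omission is certain.

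**What to change.** Amend SAP 5.5.12.1.2 and the C-SSRS rows of Table CGAI.5.4 as follows.

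- Completed suicides, and suicidal behavior reported as an SAE or as an AE leading to discontinuation, count as events in the matching behavior category whether or not a postbaseline C-SSRS exists.
- The denominator for the behavior rows is the dosed population of the period: the Safety Population in SP III and the open-label treatment population in SP IV. In SP V, where nobody is dosed, use all patients who enter the phase. At minimum, treat patients with such events as evaluable.
- A footnote identifies each event that came from a source other than the C-SSRS.
- The present evaluability rule stays for ideation and for the comparative endpoints built on the ideation score. The text should say which rule governs emergence of suicidal behavior, which is compared with C-SSRS history.

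The data are already collected. The cost is a short SAP amendment, a merge with the AE data, and a small blinded medical review to map AE terms to C-SSRS behavior categories. The drawback is some mixing of spontaneous reports with interview data; the footnote makes that visible, and limiting the added events to SAEs and AEs leading to discontinuation keeps it small.

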5.5.12.1.3. Vital Signs and Weight

Vital signs collected during the study include systolic and diastolic blood pressure, pulse, and temperature. Blood pressure and pulse measurements will be taken when the patient is in a sitting position. Three measurements of sitting blood pressure and pulse will be collected at approximately 30-60 second intervals at every visit, and the 3 sitting blood pressure measurements and 3 pulse values will be averaged and used as the value for that visit.

The number and percent of patients meeting criteria for treatment-emergent abnormalities in vital signs and weight at any time during study will be summarized. Treatment group comparisons will be performed using CMH test.

Table CGAI.5.6 displays the criteria for categorical changes of interest in vital signs and weight. The last column of the table displays the patient populations defined by baseline categories.

The criteria generally consist of two parts, an absolute threshold and a change from baseline amount.

- The absolute threshold in the criteria is based on 1) minimum postbaseline when the direction is low; 2) maximum postbaseline when the direction is high.
- The change from baseline amount in the criteria is 1) decrease from baseline (defined below and in Table CGAI.5.4) to minimum postbaseline when the direction is low;
 2) increase from baseline (defined below and in Table CGAI.5.4) to maximum postbaseline when the direction is high.

The baseline for SBP, DBP, and pulse is defined as the last non-missing baseline value during the baseline period (See Table CGAI.5.4). To be exact,

- For analyses including double-blind treatment phase, the baseline for SBP, DBP, and pulse is defined as the last non-missing value before randomization.
 The rationale for using the last available value in the baseline period is to minimize the potential confound of discontinuing or dose stabilization of medications that modulate BP and pulse during the screening phase (which is early in the baseline period).
- Similarly, for other study phases, the baseline is defined as the last non-missing value before patients enter the study phases of interest.
 This baseline definition was chosen to be consistent with the analysis approach for double-blind treatment phase as described above.

This baseline definition for SBP, DBP, and pulse applies to all analyses (both continuous and categorical) for SBP, DBP, and pulse.

The baseline and postbaseline values for temperature and weight are defined below (Table CGAI.5.4):

- For continuous analyses of temperature and weight, last nonmissing baseline during the baseline period will be used as the baseline.
- For the analyses of categorical changes of interest in temperature and weight,
 - o the baseline is defined as the minimum value during baseline period when the direction is low.
 - o the baseline is defined as the maximum value during the baseline period when the direction is high.

Table CGAI.5.6. Criteria for Categorical Changes of Interest in Vital Signs and Weight

Parameter	Direction	Criteria	Patients Population defined by Baseline Categories
Systolic BP (mm Hg)	Low	≤90 and decrease ≥20	All patients; >90; ≤90
(sitting)	High	≥140 and increase ≥20	All patients; <140, ≥140
	PCS High	≥180 and increase ≥20	All Patients; <180; ≥180
	Sustained Elevation	≥140 and increase ≥20 at 2 consecutive visits	All patients; < 140; ≥140
Diastolic BP (mm Hg)	Low	≤50 and decrease ≥10	All patients; >50; ≤50
(sitting)	High	≥90 and increase ≥10	All patients; <90; ≥90
	PCS High	≥105 and increase ≥15	All Patients; <105; ≥105
	Sustained Elevation	≥90 and increase ≥10 at 2 consecutive visits	All patients; < 90; ≥90
Diastolic BP (mm Hg) Elevation for 2 consecutive visit (sitting) meeting criteria for diagrams.		Meeting criteria for systolic BP for 2 consecutive visits or meeting criteria for diastolic BP for 2 consecutive visits or both	All Patients
Pulse (bpm) (sitting)	Low	<50 and decrease ≥15	All patients; ≥50; <50
	High	>100 and increase ≥15	All patients; ≤100; >100
	Sustained Elevation	>100 and increase ≥15 at 2 consecutive visits	All patients; ≤100; >100
Weight (kg)	Low	(Loss) decrease ≥7%	All patients
	High	(Gain) increase ≥7%	All patients
Temperature (° F)	Low	<96° F and decrease ≥2° F	≥96°F
	High	≥101° F and increase ≥2° F	<101°F

Abbreviations: BP = blood pressure; bpm = beats per minute; F = degrees Fahrenheit; kg = kilograms; mm Hg = millimeters of mercury; PCS= Potentially Clinically Significant.

5.5.12.1.4. Electrocardiogram Intervals and Heart Rate

Analyses of corrected QT (QTc) interval will be calculated using 2 correction formulas. The QTcF (msec) will be calculated with Fridericia's formula as QT/RR $^{1/3}$. The Large Clinical Trial Population Based QT Correction (QTcLCTPB) (msec) will be calculated with the formula as QT/RR $^{0.413}$. For the QTc calculations, the unit for QT is milliseconds and the unit for RR is seconds. For patients with QRS \geq 120 msecs at any time during the study, the QT and QTc interval will be excluded from the analyses. A listing of ECG data for patients with QRS \geq 120 msecs at any time during the study will be provided.

The baseline for ECG is defined as the last non-missing baseline value during the baseline period (See Table CGAI.5.4). To be exact,

• For analyses including double-blind treatment phase, the baseline for ECG is defined as the last non-missing value before randomization.

The rationale for using the last available value in the baseline period is to minimize the potential confound of discontinuing or dose stabilization of medications that modulate ECG during the screening phase (which is early in the baseline period).

 Similarly, for other study phases, the baseline is defined as the last non-missing value before patients enter the study phases of interest.
 This baseline definition was chosen to be consistent with the analysis approach for the double-blind treatment phase as described above.

This baseline definition for ECG applies to all analyses (both continuous and categorical, quantitative and qualitative) for ECG.

The baseline and postbaseline values are summarized in Table CGAI.5.4.

The number and percent of patients meeting criteria for treatment-emergent abnormalities in ECG intervals (PR, QRS, QTcF, and QTcLCTPB) and heart rate at any time during study will be summarized. Treatment group comparisons will be performed using CMH test.

Table CGAI.5.7 displays the criteria for treatment-emergent changes in ECG intervals, heart rate, and QTcLCTPB. The absolute threshold in the criteria is based on 1) minimum postbaseline when the direction is low; 2) maximum postbaseline when the direction is high.

For QTcLCTPB, the treatment-emergent low and high criteria are listed by gender and age range, based on Lilly reference ranges.

- For treatment-emergent low analyses: Patients with all normal or high values at baseline (no low values) will be included.
- For treatment-emergent high analyses: Patients with all normal or low values at baseline (no high values) will be included.
- For treatment-emergent increase analyses: Patients with a baseline and at least 1 postbaseline result will be included.

Table CGAI.5.7. Criteria for Treatment-Emergent Changes in ECG Intervals and Heart Rate

Parameter	Direction	Crite	eria	
Heart Rate (bpm)	Low	<50 and dec	crease ≥15	
	High	>100 and increase ≥15		
PR Interval (msec)	Low	<120		
	High	≥22	20	
QRS Interval (msec)	Low	<6	0	
	High	≥12	20	
QTcF (msec)	Low	Males: <330	Females: <340	
	High	Males: >450	Females: >470	
		>500 r	nsec	
	Increase	Increase >	30 msec	
		Increase >	60 msec	
		Increase >	75 msec	
QTcLCTPB (msec)	Low	Male (All ages): <330;	Female (All ages): <340	
	High	Male	Female	
		Age (yrs): criteria	Age (yrs): criteria	
		<18: >444	<18: >445	
		18-25: >449	18-25: >455	
		26-35: >438	26-35: >455	
		36-45: >446	36-45: >459	
		46-55: >452	46-55: >464	
		56-65: >448	56-65: >469	
		>65: >460	>65: >465	
		>500 msec		
	Increase	ncrease Increase >30 msec		
		Increase >60 msec		
		Increase >	75 msec	

Abbreviations: bpm = beats per minute; msec = milliseconds.

In addition, a descriptive summary of qualitative ECG abnormalities will be conducted which will include summaries of 11 ECG categories (Axis, Rhythm, Conduction, Ischemia, Infarction, Injury, Morphology, U-waves, T-waves, ST Segment, and Other Abnormalities) of qualitative findings at any time postbaseline. A category is a collection of possible descriptions (findings) of 1 qualitative aspect of an ECG. A category name is the name of the qualitative aspect of the ECG (for example, Rhythm, Conduction, Morphology, Ischemia, and so forth). A finding is 1 of the possible specific descriptions (for example, Sinus Bradycardia, Acute Septal Infarction) within a category.

The summaries of the 11 ECG categories will exclude ECGs with any of the following: overall ECG could not be evaluated by the cardiologist, lead reversals or <9 leads, nonmatching demographic data, and those suggesting patient identification errors.

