9.5.5. Electrocardiogram Intervals and Heart Rate

Analyses of corrected QT interval will be calculated using two correction formulas. The QTcF (measured in milliseconds [msec]) will be calculated with Fridericia's formula as QT/RR ^{1/3}. The Lilly Large Clinical Trial Population Based QT Correction (QTcR) (msec) will be calculated with the formula as QT/RR ^{0.413}. The number and percent of patients meeting criteria for treatment-emergent abnormalities in ECG intervals (pulse rate [PR], QRS, QTcF, and QTcR) and heart rate at any time during study will be summarized. Treatment group comparisons will be performed using the Fisher's exact test.

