5.5.12.2. Continuous Safety Measures

Analyses of continuous safety data will be conducted for SP III, SP III/IV, and SP III/IV/V on patients who have a baseline and at least 1 postbaseline observation. In those analyses, values from unscheduled visits will not be included, and only values collected at scheduled visits will be used.

For continuous safety measures (including laboratory measures, vital signs and weight, ECG intervals and heart rate), changes from last baseline value to LOCF endpoint during SP III, will be assessed using an ANCOVA model with treatment, baseline medication overuse, concurrent prophylaxis use, and baseline value as covariates. If repeat laboratory values exist at the same scheduled visit, only the last nonmissing laboratory value at a visit (selected by using the variable with highest lab sequence ID) will be used in the ANCOVA analysis for mean change from last baseline value to LOCF endpoint.

For vital signs of blood pressures and pulse rate, as well as weight (when applicable), the mean change from baseline will be analyzed for SP III, SP III/IV, and SP III/IV/V using an MMRM analysis. The analysis will include the fixed categorical effects of treatment, month, baseline medication overuse, concurrent prophylaxis use and treatment-by-month interaction, as well as the continuous fixed covariates of baseline value and baseline-by-month interaction.

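### The QRS rule removes all of a patient's QT/QTc data because of any one wide-QRS ECG in the study, so an ECG at screening or from a later phase can delete a valid Visit 7 QTc from the treatment comparisons

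*SAP*

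**What the plan says.** SAP section 5.5.12.1.4 excludes QT data by patient. Where QRS is 120 or more "msecs at any time during the study, the QT and QTc interval will be excluded from the analyses". The next sentence provides "A listing of ECG data for patients with QRS" at or above that limit, so these patients' ECG data are listed.

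The same section plans to summarize, and compare by CMH test, patients "meeting criteria for treatment-emergent abnormalities in ECG intervals (PR, QRS, QTcF, and QTcLCTPB) and heart rate at any time during study". Table CGAI.5.7 makes QRS of 120 msec or more a treatment-emergent High finding in its own right. For the increase categories the section says: "For treatment-emergent increase analyses: Patients with a baseline and at least 1 postbaseline result will be included".

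SAP section 5.5.12.2 adds an ANCOVA of change to LOCF endpoint in SP III: "For continuous safety measures (including laboratory measures, vital signs and weight, ECG intervals and heart rate" are all covered. SAP section 5.5.12.1 plans CMH comparisons of categorical safety measures for SP III and for SP III/IV; SP IV and SP V alone are descriptive.

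The protocol's Appendix 2 fixes the tracings: "Electrocardiograms (ECGs) will be performed at Visit 1, Visit 3, Visit 7, Visit 10, Visit 16, and Visit 18 or early termination". Protocol section 9.5.5 plans to summarize "The number and percent of patients meeting criteria for treatment-emergent abnormalities in ECG intervals" and states no QRS exclusion.

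**The concern.** A QTc from a tracing with wide QRS is hard to interpret, which is a reason to set that tracing aside. It is not a reason to set aside the same patient's tracings with normal QRS, and the SAP gives no rationale for doing so.

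Two things are at stake. First, part of the trigger is a post-baseline safety outcome that the SAP itself tabulates. Membership of the QTc analysis set then depends on what happened after randomization, and denominators could differ by arm for reasons related to treatment. Second, the trigger has no time limit. Who counts in the double-blind QTc comparison can depend on ECGs taken months later, when former placebo patients who continued are also receiving LY2951742. The QTc outlier categories (above 500 msec, increase above 60 or 75 msec) are likely to hold few patients, so losing even one who had such a value would be visible.

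**Working it through.** The plan states no count or rate for this exclusion, so there is no figure to reproduce. The check is of wording and timing, followed by an illustration of size.

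**1. By patient or by tracing?** The QRS rule takes patients as its subject and covers the whole study. The last paragraph of the same section, on the 11 qualitative ECG categories, instead removes individual ECGs with technical faults. The section thus words a per-tracing exclusion differently when it wants one. Nothing elsewhere limits the QRS rule to the affected tracing or to baseline.

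**2. Which tracings count?** There are six scheduled ECGs: Visits 1 and 3 before the first dose, Visit 7 at the end of SP III, Visits 10 and 16 in SP IV, and Visit 18 (or early termination) in SP V. For a completer, one wide-QRS tracing costs six scheduled QTc records (four after the first dose) under the plan's rule, and one under a per-tracing rule.

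**3. Effect on SP III, by where the wide QRS occurs.**
- Visit 1 or 3 only: the plan's rule drops a valid Visit 7 QTc. A per-tracing rule keeps it, with the other pre-dose ECG as baseline.
- Visit 7: both rules lose the Visit 7 QTc, and the patient leaves the SP III analysis unless there is an unscheduled ECG.
- Visit 10, 16 or 18 only: the plan's rule drops a valid Visit 7 QTc from SP III/IV, and from SP III if the later ECG is in the database at the lock. A per-tracing rule keeps it.

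**4. What is known at the lock?** SAP section 5.8.1.2 makes the interim analysis #2 results final for the double-blind phase. The same lock reports ECG parameters for SP IV and some efficacy measures up to Month 9 of SP IV, so some patients will have later ECGs by then and others will not. Whether a later ECG removes a patient from SP III would depend on enrollment date, or on whether the programmer uses SP IV/V data for an SP III table. The SAP does not say.

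**5. Illustration of size.** Inputs: N = 1140 (SAP section 5.2), six ECGs per patient, and a per-ECG probability p of QRS of 120 msec or more, which is an assumption. Everyone is taken to complete all six ECGs.
- Fully persistent finding: excluded = 1140 × p.
- Tracings independent: excluded = 1140 × [1 − (1−p)^6].
- Of these, first wide at Visit 10 or later: 1140 × [(1−p)^3 − (1−p)^6].
- Of these, normal at Visit 7 but wide on another ECG: 1140 × (1−p) × [1 − (1−p)^5].

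| p (assumed) | Excluded, persistent | Excluded, independent | First wide at Visit 10 or later | Valid Visit 7 QTc lost, independent |
|---|---|---|---|---|
| 0.25% | 2.9 | 17.0 | 8.5 | 14.1 |
| 0.5% | 5.7 | 33.8 | 16.8 | 28.1 |
| 1% | 11.4 | 66.7 | 32.9 | 55.3 |
| 2% | 22.8 | 130.1 | 63.1 | 107.3 |

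For p = 0.5%: 1140 × 0.995 × (1 − 0.995^5) = 1140 × 0.02463 = 28.1. Under full persistence the last two columns are zero, because Visit 7 is then wide as well. The truth lies between the two extremes, and the documents do not say where. At the SP III lock only part of the later-ECG share would yet apply.

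**The case against.** The strongest reply is that a per-tracing rule changes little in SP III. There is one scheduled post-dose ECG in that phase, and if QRS is wide on it, its QTc is dropped either way. That stands: the case of a patient whose QRS widens on treatment by Visit 7 is not rescued. The rules differ in SP III only when the trigger is before the first dose or after Visit 7, or when an unscheduled ECG exists. A per-tracing rule also still conditions on post-baseline QRS; only a baseline-based rule avoids that.

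A reader might infer that the SP III result would keep shifting as SP IV and SP V proceed. The documents do not support that. SAP section 5.8.1.2 fixes the double-blind results at interim analysis #2, and section 5.8.1.3 reserves re-running for reports that include later phases. What remains is that the exclusion set is not fully defined at that lock.

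A reader might also infer that drug-related QTc events would be hidden. That goes too far. The rule covers placebo and pre-dose ECGs as well, and nothing in the documents suggests a drug effect on QRS. The excluded patients' ECG data are listed. QRS of 120 msec or more is still tabulated and compared, the qualitative summary (including Conduction) is not subject to this rule, and ECG findings leading to a diagnosis are reported as adverse events (protocol section 8.4.1). None of this returns valid QTc values to the rates, but the patients can be seen.

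Finally, the rule might have been meant per tracing. If so, the sentence still needs correcting, because it does not say that.

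**Conclusion.** The point holds in limited form. As written, one wide-QRS ECG anywhere in the study removes all of a patient's QT/QTc data. A screening ECG, or an SP IV/V ECG already in the database at interim analysis #2, can therefore delete a valid Visit 7 QTc from the randomized SP III comparison. A later wide-QRS ECG can delete it from the SP III/IV comparison. The SP III exclusion set is not fully defined at the lock that makes those results final, so two programmers could reach different denominators.

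The effect is probably small, and its size cannot be derived from the documents. The table rests on an assumed p and two extreme patterns. It counts excluded patients, not lost QTc events, which would also require an outlying QTc on a tracing with normal QRS. This is a minor correction to a safety display and does not touch the primary or key secondary analyses.

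**What to change.** Rewrite the sentence in SAP section 5.5.12.1.4 in one of two ways:

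- **Per tracing:** omit QT and QTc only for individual ECGs with QRS of 120 msec or more, and keep the patient's other ECGs.
- **Per patient, at baseline:** if a patient-level exclusion is wanted, base it only on pre-dose QRS. This also avoids conditioning on a post-baseline outcome.

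In either case, state that no ECG from after a study phase decides exclusion from that phase's analysis. Keep the planned listing, and report the number of patients and tracings excluded by arm for each QTc analysis.

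The cost is one sentence, one changed filter and one extra count. Each option has a drawback. The per-tracing rule still drops a wide-QRS Visit 7 tracing in SP III, and patients then contribute unequal numbers of ECGs. The baseline-only rule keeps some QTc values from wide-QRS tracings, which are harder to interpret.
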